13.4. Restrictions

The volunteers will be requested not to undertake vigorous exercise during the 2 days before the initial screening laboratory tests until after the final laboratory safety tests.

When confined to the clinical centre, the volunteers have to avoid from alcohol starting one week before hospitalization day until the last blood sampling of period. Smoking will not be permitted during the study of blood sampling during hospitalization of study. Chewing gum is not allowed. No foods and beverages containing caffeine or other methylxanthines (coffee, tea, coke, chocolate) and fruit-juice from 2 days prior to dosing until the last blood sampling of study will be allowed. No grapefruit containing products from 7 days prior to the dosing until the last sampling will be allowed. The volunteers will abstain from food and beverages from 21:00 on the hospitalization evening until final examination. (Subjects will not be allowed to drink water between 1 h before to 1 h after administration, except while dosing). The total intake of water on the days of dosing during hospitalization will be maximum 1.5 L, beginning 1 hour post-dosing.

For the ambulatory phases of the study, volunteers will be requested to abstain from alcohol containing foods and beverages for the study starting 24 hours before the initiation of the study until confinement to the clinic. Upon admission to the clinic for study, all volunteers will undergo an alcohol breath test and drug screening in the urine (see 13.1). Volunteers with a positive result of the test will be discontinued from the study.

13.5. Drug Administration

The following treatments will be administered:

Test Drug; Favicovir 200 mg Film Tablet (Atabay-Turkey)

Reference Drug; Avigan 200 mg Film Tablet (Toyama Chemical Industry Co.Ltd./Japan)

The precise instructions for drug administration are given in Ethical Committee (EC) and Ministry of Health (MoH) submission file.

Immediately after pre-dose sampling, the volunteers will swallow 1 tablet of the test drug or 1 tablet of the reference drug (favipiravir each case) with 240 mL water. After the washout period; in Period II, the subjects will be administered by the other drug that they will not administered in the Period I.

This will be followed by a mouth check. The investigator or the co-investigator will administer the study medication and this will be supervised by a second medical professional to ensure the correct drug administration.

The subjects will be dosed in ascending numerical order according to the randomisation list whilst sitting position and they will be instructed to remain in **sitting position** in bed for **4 hours** after drug administration without lying in bed for each period. In this interval $(t_{0.17}$ - $t_{4.00})$; the blood samples will be performed in bed and lunch will be provided on bed.

13.6. Dietary Regimen

An evening meal (total caloric value of approximately 1200 kcal) will be served no later than 21:00 in the 1st hospitalization day (Day 0) in study.

Period I and **Period II:** In treatment day (Day 1 and Day 3);

Study Code: NOV2020/01917
Clinical Study Protocol
Version: 1.0

A standard lunch (total caloric value is approximately 1200 kcal) will be provided 4 hours after dosing in study.

A standard evening meal (total caloric value is approximately 1200 kcal) will be provided 10 hours after dosing in study.

A standardised light breakfast will be served approximately 21:30 p.m.

Also standard breakfast, standard lunch, standard evening meal and a standardised light breakfast will be served in Day 2. In 4th day of the study standard breakfast and lunch will be served.

The same meal composition has to be served in all study of the trial. This will be documented in the CRF.

13.7. Blood Sampling for Drug Analysis

Venous blood will be drawn at the following times:

Period	Day	Time (hour)*	Tube No
1-2	1	t _{0.00}	P01
		t _{0.17}	P02
		t _{0.25}	P03
		$t_{0.50}$	P04
		$t_{0.75}$	P05
		$t_{1.00}$	P06
		t _{1.33}	P07
		t _{1.66}	P08
		t _{2.00}	P09
		t _{2.50}	P10
		t _{3.00}	P11
		t _{3.50}	P12
		t _{4.00}	P13
		t _{5.00}	P14
		t _{6.00}	P15
		t _{8.00}	P16
		t _{10.00}	P17
		t _{14.00}	P18
	2	t _{24.00}	P19

^{*} In the statistical analysis, if the deviation in the planned sampling time is 1 minute and within the range of \pm 5% deviation, the values will be used without any correction.

8 mL blood samples will be drawn at predetermined sampling times during the clinical study to determine plasma **favipiravir** concentrations.

Note: Only in Period I; at t_0 the blood sample amount will be 20 mL and this sample will be divided into tubes and one of this tube will be used for the anti-coagulant validation purpose during the analytical validation process. This plasma sample will send to Novagenix with master and back-up samples.

The blood samples will be taken by a short intravenous catheter. The blood samples will be collected into polypropylene tubes using K_2 EDTA as anti-coagulating agent. The total amount of blood taken from each subject will be approximately 358 mL.

[Including "The Heparinised Discarded Blood (approximately 10 mL during the study)", "Blood for Entry/Final examinations Tests (*approximately 32 mL)" and "Other Repeat Clinical Laboratory Tests that may be deemed necessary during the study"].

*At entry examination the blood sample amount will be 20 mL and 8 mL sample of 20 mL sample will be divided into tubes and one of this tube will be used for the anti-coagulant validation purpose during the analytical validation process. This plasma sample will send to Novagenix with master and back-up samples. At final examination the blood sample amount will be 12 mL and only will be used for clinical laboratory tests.

After sampling the blood samples for pharmacokinetic analysis, the tubes will be immediately refrigerated at 2 - 8°C and will remain there for not more than 30 minutes. After centrifugation (3.000 rpm, 4 - 6°C, 10 min), the separated **plasma** from each sample will be transferred into two 3 mL transparent, polypropylene tubes per sample (at least 1.5 mL per tube). All the aliquoted plasma samples will be flash freezing immediately. The flash frozen samples (aliquoted plasma samples) will be transferred to a deep-freezer and stored at -70°C.

At the end of the study one aliquot will be shipped on dry ice (solid CO₂) according to the sample transport SOP of FARMAGEN-Good Clinical Practice and Research Center by courier for the determination of plasma drug concentrations to the analytical laboratory:

Novagenix Bioanalytical Drug R&D Centre [name]

As precautionary measure, the other aliquot will at first be retained at the clinical unit in case that any adverse conditions, for example due to transport damage of the first shipment. Once the bioanalytical laboratory confirms receipt of the first shipment, the second set of aliquots will be sent.

The samples will be packed on dry ice for transport, no interruption of the freeze chain is allowed and also data loggers will be included for temperature recording.

All labels for blood and plasma samples will be provided by NOVAGENIX and will contain the following information: active ingredient name, study code, subject number, period, tube number and time (e.g. 2 h post-dosing). An example is given below:

Favipiravir				
Study #: NOV01917				
Subj # 1	Period: 1			
Time: 0 h P#: P1				

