6. STUDY FLOW CHART

	SC	CREENING A	AND ISOLA	ΓΙΟΝ	PERIOD I		PERIOD II		*Final	
Study Day:	1st DAY screening	2 nd DAY (isolation)	3 rd DAY (isolation)	4 th DAY (isolation)	5 th DAY Hospitaliz ation day (Day 0)	6 th DAY 1 st dosing day and blood sampling (Day 1)	7 th DAY blood sampling (t _{24.00}) Wash-out day/ (Day 2)	8 th DAY 2 nd dosing day and blood sampling (Day 3)	9 th DAY blood sampling (t _{24.00}) (Day 4)	9 th DAY Final examination
Informed consent	•									
Covid-19 PCR Test	•				•					•
Inclusion criteria	•				•					
Demography (Birth date, ethnic group, gender, height, weight, BMI)	•									
"Medical/Surgical history HBsAg, anti-HCV,	•									
HIV anti-HCV,	•									
ECG	•									•
Clinical examination (Physical examination)	•									•
Clinical chemistry, haematology, urinalysis	•									•
Blood pressure, pulse rate	•	•	•	•	•		•			•
Body	•	•	•	•	•	•	•	•	•	•
temperature ^O Drug abuse screening**	•									
Alcohol breath test	•									
Check of restrictions, diet					•	•	•	•		
Exclusion criteria and Withdrawal of volunteers	•	•	•	•	•	•	•	•	•	
Hospitalization day					•					
Randomisation	•									
Drug administration						•		•		
Blood sampling*** (0-24.00 h)						•	•	•	•	
Adverse event questioning****					•	•	•	•	•	

^{*} The final examination will be carried out on the day of last blood sampling.

[°] Body temperature monitoring will be performed at the following times: at "screening/isolation days", "hospitalisation day (Day 0)", "during study period" and "final examination".

^{**} For amphetamines, cannabinoids, benzodiazepines, cocaine, opioids, and barbiturates.

^{***}Blood sampling points (for each period): at pre-dose (20 mL only in Period I) and at 0.17, 0.25, 0.50, 0.75, 1.00, 1.33, 1.66, 2.00, 2.50, 3.00, 3.50, 4.00, 5.00, 6.00, 8.00, 10.00, 14.00, 24.00 hours post-dose (1 x 8

Study Code: NOV2020/01917
Clinical Study Protocol
Version: 1.0

mL each; totally 19 blood sample points)

1. Only in Period I; at t_0 the blood sample amount will be 20 mL.

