7.3. Pharmacokinetics

Absorption and Distribution

Following oral administration favipiravir reaches peak plasma concentrations in approximately 0.5 hours. After a single 200 mg dose of oral favipiravir tablet to Japanese healty volunteers C_{max} and AUC_{0-t} were 8.39 $\mu g/ml$ and 19.67 $\mu g.h/ml$ respectively. The Cmax of favipiravir was linear in the dose range from 30 to 1200 mg, while the AUC values at the dose of ≥ 600 mg remained higher than the value expected from the dose-proportional relationship. It is reported than the pharmacokinetics in the dose range in which the pharmacokinetic profiles were linear were compared between healthy adult subjects in Japan and the US (when the doses were normalized on the basis of a body weight of 60 kg).

When oral tablet of favipiravir was given with a high-fat meal a decrease in Cmax and AUC was observed.

Favipiravir is 53.4%-54.4% bound to plasma proteins.

Metabolism and Excretion

Favipiravir M1 and glucuronide conjugate of favipiravir (M2) were found in the human plasma and urine obtained after single-dose administration.

The elimination of favipiravir largely depends via renal excretion with a mean plasma elimination half-life ($t_{1/2}$) of 1.5 hours.

Some pharmacokinetics parameters of oral Favipiravir tablet are shown in the following table:

t _{max} (h)	Cmax (μg/mL)	Protein binding (%)	t _½ (h)	Excretion
0.5	8.39 (200 mg single dose)	53.4-54.4	1.5	via renal excretion

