13.2. Special Procedures

Special procedures due to the Covid-19 outbreak will be done as described in Appendix VII.

Study drugs will be administered on the Day 1 and Day 3 (as given in the Study Flow Chart provided in section 6). The subjects will be fasted overnight (minimum of 10 hours) and administrations will take place in the morning approximately at 08:00 a.m. and the exact time will be recorded on CRFs.

The subjects will remain fasting until 4 hours after administration. Subjects are not allowed to drink water from 1 h before until 1 h after administration, except that while dosing. Subjects will be dosed in sitting position and they will be instructed to remain in sitting position in bed for 4 hours after drug administration without lying in bed for each period. In this interval $(t_{0.17}$ - $t_{4.00})$; the blood samples will be performed in bed and lunch will be provided on bed.

During this study all clinical unit personal will be checked daily by Covid-19 PCR test for safety

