18. PHARMACOKINETIC EVALUATION

Pharmacokinetic parameters of **favipiravir** will be determined using non-compartmental methods from measured plasma concentrations.

For each treatment (**Test Drug** or **Reference Drug**) and each volunteer participating completely in this **single-dose**, **two period**, **cross-over study** the following pharmacokinetic parameters will be calculated:

Primary pharmacokinetic parameters:

C_{max}: Maximum observed plasma concentration

AUC_{0-tlast}: Area under the plasma concentration-time curve from zero to the last measurable concentration, calculated by the linear log trapezoidal rule.

Secondary pharmacokinetic parameters:

 $AUC_{0-\infty}$: Area under the plasma concentration-time curve, calculated by extrapolation to infinity.

 t_{max} : Time to maximum observed plasma concentration

 $t_{1/2}$: Terminal half-life

Additional pharmacokinetic parameters:

MRT: Mean residence time

 λ_z : Terminal rate constant.

For pharmacokinetic calculations, the program package **Phoenix WinNonlin (Version 8.1, Certara L.P.)** or above will be employed. Phoenix WinNonlin will also be used to generate concentration/time plots.

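### The sampling-time footnote in 13.7 keeps draws inside the tolerance at planned time; actual elapsed times would remove a small, avoidable error in AUC and t1/2

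*Combined protocol and SAP*

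**What the plan says.** The sampling table in section 13.7 has a footnote attached to its time column, and it is a rule for the statistical evaluation. Its condition begins "if the deviation in the planned sampling time is 1 minute and within the range of" and goes on to name a band of 5% either side. For draws that meet this condition, the footnote ends "5% deviation, the values will be used without any correction". It does not say what correction applies to draws outside the tolerance.

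Section 18 says the parameters "will be determined using non-compartmental methods from measured plasma concentrations", with AUC0-tlast "calculated by the linear log trapezoidal rule". It does not say whether time means planned or actual time, and section 19 adds nothing. The footnote is therefore the only time-basis rule in the plan.

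On recording, section 13.2 says administration takes place "in the morning approximately at 08:00 a.m. and the exact time will be recorded on CRFs". That concerns dosing. No visible section makes the same commitment for blood draws, although the footnote presupposes that deviations are known.

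**The concern.** Taking *without any correction* to mean that the planned time is kept, a draw inside the tolerance enters the calculation at a time when it was not taken. AUC0-tlast (primary) and AUC0-∞ and t1/2 (secondary) then carry an error made by the analysis rule, not by the data. Draws outside the tolerance get some unspecified correction, so one profile can mix planned and corrected times.

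How much this matters depends on how the footnote is applied. The limits of 1 minute and 5% are very different over a 24 h grid, and an analyst who lets the 5% limit govern would accept far larger deviations than one who requires both limits to hold. That choice is better settled before the treatment code is opened.

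**Working it through.** The footnote states a tolerance and not a calculated result, so there is no figure of the plan to reproduce.

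**1. The tolerance in minutes.** 5% of a planned time t (hours) is 0.05 × 60 × t = 3t minutes, which equals 1 minute at t = 0.333 h. The text says the deviation *is* 1 minute; I read this as up to 1 minute.

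| Planned time (h) | 5% (min) | Both limits hold (min) | Either limit suffices (min) |
|---|---|---|---|
| 0.17 | 0.51 | 0.51 | 1 |
| 0.25 | 0.75 | 0.75 | 1 |
| 0.50 | 1.5 | 1 | 1.5 |
| 2.00 | 6 | 1 | 6 |
| 4.00 | 12 | 1 | 12 |
| 10.00 | 30 | 1 | 30 |
| 14.00 | 42 | 1 | 42 |
| 24.00 | 72 | 1 | 72 |

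With both limits required, 5% governs at 0.17 h and 0.25 h and 1 minute governs from 0.50 h on.

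**2. Model for the size.** Inputs from section 7.3: t_max 0.5 h, t1/2 1.5 h, AUC 19.67 µg·h/mL (AUC cancels from percentage errors). The one-compartment form is my assumption:

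C(t) = AUC · ke · ka/(ka − ke) · (e^(−ke·t) − e^(−ka·t)), with ke = ln 2/1.5 = 0.462 per h and ka = 5.37 per h, solved from ln(ka/ke)/(ka − ke) = 0.5.

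AUC is the linear-log trapezoid of section 18. Half-life is a log-linear fit to 6–14 h. Samples are taken as measurable to 14 h; the documents shown give no limit of quantification. Each profile is drawn at deviated times and entered at planned times.

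**3. Both limits required (literal reading).**
- All draws at the late limit: AUC −0.38%. All at the early limit: +0.37%. With t_max varied from 0.25 to 1.0 h the size runs from about 0.2% to 0.5%.
- Independent uniform deviations: AUC SD 0.14%; t1/2 95% range 1.495–1.505 h, since 0.005/1.5 = 0.3%.

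**4. ±5% window.**
- Uniform shift: each interval is mis-scaled by the same factor, so AUC is multiplied by 1/1.05 = 0.952 (−4.8%) if late and 1/0.95 = 1.053 (+5.3%) if early. The fitted half-life becomes 1.5/1.05 = 1.43 h or 1.5/0.95 = 1.58 h.
- Independent uniform deviations: AUC SD about 0.9%; t1/2 95% range about 1.36–1.67 h. With the last measurable sample anywhere from 8 h to 24 h, the AUC SD stays at 0.9–1.0% and the SD of t1/2 runs from 4.7% to 6.6%.
- One 10 h draw 30 min late: its concentration is multiplied by 2^(−0.5/1.5) = 0.794, a 21% drop, but AUC moves by only −0.28%, because C(10 h) is about 1.4% of C_max in this model.

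**5. Effect on the bioequivalence test.** C_max does not depend on the time assigned. Section 19.2 gives a CV of 17% for C_max only; I use it as a stand-in for AUC. Adding 1% random timing error gives √(17² + 1²) = 17.03%. For the 2×2 two one-sided tests with 30 subjects (SE = √ln(1 + CV²) · √(2/30), 28 df, limits 80–125%) and an assumed true ratio of 0.95, power is 98.6% both with and without the added error.

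**6. With actual times.** The difference between planned-time and actual-time results is zero under either reading. Only ordinary trapezoid error remains.

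**The case against.** The strongest reply is that the footnote is a coherent, strict rule. Its two limits are joined by *and*; each governs part of the grid, and they cross at 0.33 h. Any deviation beyond 1 minute then falls outside the rule being criticised, and what remains is trivial. This stands: a reader might infer that the limits contradict each other and that the rule cannot be read consistently, and the text does not support that.

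A reader might also infer that AUC could be biased by 5% and the bioequivalence conclusion put at risk. That needs the ±5% window in place of the literal wording, and every draw in a profile off by the full 5% in one direction. Subjects are hospitalised throughout, and nothing in the documents suggests such drift. Even then, a shift common to both products cancels in the test/reference ratio, and a period-wide shift is largely absorbed by the period term in the ANOVA. Similarly, the 21% change in a late 10 h concentration is correct but has little weight in AUC.

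Finally, keeping the planned time is an inference from the footnote, not its stated wording, and the use of actual times depends on draw times being recorded. Both points stand; the second belongs in the fix. They do not remove the case for change, because the footnote is the only time-basis rule, its wording leaves room for the wide window, and actual times are better under either reading.

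**Conclusion.** The point holds as a minor improvement. On the literal reading the avoidable error is about 0.4% on AUC with all draws at the limit, and about 0.3% on t1/2. If the tolerance is applied as a ±5% window, it is about 0.9% SD on AUC for random deviations and a 95% range of about 1.36–1.67 h for a true 1.5 h half-life; the shift of about 5% in AUC is a worst case. The most exposed result is t1/2, a secondary variable. The bioequivalence decision is little affected.

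The sizes rest on the assumed one-compartment curve, uniformly distributed deviations, samples measurable to 14 h, and reading the footnote as keeping planned times.

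**What to change.** Replace the footnote in section 13.7 with:

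*The exact clock time of every blood draw will be recorded in the CRF, and actual elapsed time from dosing will be used for every sample in calculating AUC0-tlast, AUC0-∞, t_max, λz, t1/2 and MRT; planned times are used only for mean concentration tables and plots.*

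Repeat the time basis in section 18. If a tolerance is still wanted, keep it only for listing timing deviations, and state whether both limits or either limit must be met.

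The cost is a sentence of text and the import of actual instead of planned times into the pharmacokinetic software. If the CRF (Appendix 2, not available here) has no field for draw time, one must be added; checking any tolerance needs that field anyway. Sampling schedule, sample size and statistical test do not change.

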13.8. Endpoint(s) For The Study

Primary Endpoint: AUC_{0-tlast} and C_{max} of **favipiravir**

Secondary Endpoint: AUC_{0- ∞}, $t_{1/2}$, t_{max} of **favipiravir**

Safety Endpoints: Adverse events, clinical and laboratory examinations.

14. PREMATURE DISCONTINUATION

The conditions for premature discontinuation of the trial in some particular volunteers or in general are summarized in this chapter.

14.1. Withdrawal of Volunteers

Volunteers may be withdrawn for the following reasons:

- at their own request with or without giving reasons,
- at the discretion of the investigator for reasons of medical prudence.

In either event, the Sponsor will be immediately notified and the date and reasons for the withdrawal will be clearly stated in the volunteer's CRF.

Volunteers must be withdrawn under the following circumstances:

• if personal circumstances suggest that the visits required by the protocol cannot be guaranteed any longer,

• if Covid-19 PCR test result is positive, the volunteer(s) will be dropped out from study.

- if adverse events (including intercurrent illnesses) develop, which rule out continuation of the study medication, or, due to impaired validity of the results, make it appear inadvisable to further participate in the study,
- if subjects who have intaked or administrated of any prescribed systemic or topical medication (including OTC medication) within **2 weeks** of the start of the study (except singles doses of analgesics which have no drug interaction with study products) given in case of an adverse event (e.g. headache) during the study,
- if circumstances defined as exclusion criteria are registered,
- if administration of any drug is necessary, which is not permitted according to the exclusion criteria (see section 11.2), independently of its necessity due to the occurrence of adverse events (including intercurrent illnesses) or of its use due to other reasons,
- if vomiting occurs at or before 2 times median t_{max}.
- if diarrhea exists during screening and /or medication day.

14.2. Replacement of Drop-outs

A total of **30** volunteers will be enrolled in the trial. If drop-out exists in isolation or in study period, then these dropouts **WILL NOT BE** replaced.

For each volunteer being withdrawn from the study prior to regular termination of the individual study period, due to any reason, a complete final examination has to be performed on the day of drop-out, as far as possible with regard to the volunteer's health conditions and as far as necessary with regard to safety aspects and the validity

of study results. The reason for withdrawal has to be documented in the case report form and in the volunteer's medical records.

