10. DESIGN

In this open-label, randomised, single-dose, two period, cross-over study, 30 healthy male subjects (intention to treat population) will receive one single oral dose of 200 mg favipiravir (one tablet of the test drug or one tablet of the reference drug) after an overnight fasting in each period according to a sequence determined by randomisation [In each study period, subjects will take different products (either one dose of Test Drug or one dose of Reference Drug)].

Data of **the subjects** who have completed the study according to the Clinical Study Protocol (per protocol population for pharmacokinetic evaluation) will be used for analytical, pharmacokinetic and statistical evaluation.

Test Drug: "Favicovir 200 mg Film Tablet" is manufactured by Atabay Kimya San. ve Tic. A.Ş., Turkey and is will be licensed by Atabay Kimya San. ve Tic. A.Ş., Turkey.

Reference Drug: "Avigan 200 mg Film Tablet" is manufactured and licenced by Toyama Chemical Industry Co Ltd.-Japan.

In study period, the subjects will be admitted to the FARMAGEN Clinical Unit in the evening (18:00) prior to morning of the administration of medication after screening and isolation period as described in Appendix VII.

Volunteers will be confined to the clinical unit and dosing will occur under conditions of hospitalization. Medications will be orally administered at approximately at 8:00 (t=0) after an overnight fasting (at least 10 hours in fasting). The lunch will be 4 hours post dosing and the dinner will be 10 hours post dosing. Blood sampling for the determination of favipiravir plasma concentrations will be drawn at specified time points. In study period including wash-out period, volunteers will be hospitalized in FARMAGEN Clinic Unit. After taking the last blood sample in 2nd period and carried out the post-study and final examination, the subjects will be allowed to leave the clinic.

An overview of the study procedures is given in the Study Flow Chart provided in section 6.

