11. SELECTION OF VOLUNTEERS

11.1. Inclusion Criteria

Only volunteers fulfilling all of the following criteria should be enrolled in the present trial:

- 1. Healthy Caucasian male subjects aged between 20 and 40 years,
- 2. Non smokers or smoking maximum 5 cigarettes a day, those who won't smoke or drink coffee during the study period,
- 3. Two Negative Covid-19 PCR test# results.
- 4. Negative alcohol breath test results,
- 5. Normal physical examination at screening visit,
- 6. Having the Body Mass Index ranged between 18.5-30 kg/m² (see Appendix I) which is in the desirable range according to the age,
- 7. Ability to communicate adequately with the investigator himself or his representatives,
- 8. Ability and agreement to comply with the study requirements,
- 9. Normal blood pressure and heart rate measured under stabilised conditions at the screening visit after at least 5 minutes of rest under supine position: SBP within 100 to 140 mmHg, DBP within 60 to 90 mmHg and HR within 50 to 90 bpm,
- 10. Normal/acceptable 12-lead electrocardiographic results at least after 5 minutes of rest,
- 11. Laboratory results within normal range or clinically non-significant (CBC, glucose, urea, uric acid*, creatinine, estimated GFR (eGFR), total bilirubin, sodium, potassium, calcium, chloride, SGOT (AST)*, SGPT (ALT)*, GGT*, alkaline phosphatase, total protein and urinalysis), drug addiction scanning in urine results in negative (amphetamine, barbiturate, benzodiazepine, cannabinoid, cocaine, opiate),
 - * SGOT (AST), SGPT (ALT), GGT and uric acid levels should be within normal range.
- 12. Understanding of the study and agreement to give a written informed consent according to section 20.3.
- 13. Understanding of that he and his partner will use a practice adequate contraception during the study and at least 7 days after the study.

 $^{\#}$ One of the Covid-19 PCR test will be applied on examination day, the other will be applied on the 5^{th} isolation day

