13.3. Daily Activities during the Trial

Entry examination:

The entry examination will be carried out on the day of screening of the trial as described in Appendix VII. The following parameters will be documented:

- Written Informed consent
- Inclusion criteria (according to protocol)
- Exclusion criteria (according to protocol)
- Demographic data (date of birth, height, weight, gender, BMI)
- Anamnestic data (medical history, relevant previous diseases)
- Clinical screening and examination (clinical state: body temperature, BP, PR, ECG, registration of pathological findings, if any, clinical chemistry*, Covid-19 PCR test, haematology, HB_sAg, HIV-Ab, HCV-Ab, drug screening, alcohol breath test, urinalysis).

*SGOT (AST), SGPT (ALT), GGT and uric acid levels should be within normal range.

Period 1:

- Interview (possible presence of exclusion criteria and/or adverse events)
- Standardised dinner will be served before dosing on day 0 (between 18:00 p.m. to 21:00 p.m.)
- Blood samples will be collected before dosing on day 1 with separation of plasma.
- Treatments will be given according to randomised administration [single oral dose of 1 tablet of the test drug or 1 tablet of the reference drug] with compliance check (approximately 08:00 a.m.)

• Blood sampling (0.17-24.00 hours) will be done after drug administration with separation of plasma

- Standardised lunch will be served at 4 hours after the dosing (between 12:00 p.m. to 13:00 p.m.)
- Standardised dinner will be served at 10 hours after the dosing (between 18:00 p.m. to 19:00 p.m.)
- Standardised light breakfast will be served at approximately 21.30 pm.
- Questioning for and registration of adverse events at hospitalisation day (Day 0), pre dose and 1.00, 4.00, 8.00, 14.00, 24.00 hours post-dose*.
- Standardised breakfast, lunch, dinner and light breakfast will be served on Day 2 (including wash-out period)

Note: Covid-19 PCR test will be done at Day 0.

Period 2:

- Interview (possible presence of exclusion criteria and/or adverse events)
- Standardised dinner and light breakfast will be served before dosing day (at 18:00 p.m. and 21:30 p.m.respectively)
- Blood samples will be collected before dosing with separation of plasma.
- Treatments will be given according to randomised administration [single oral dose of 1 tablet of the test drug or 1 tablet of the reference drug] with compliance check (approximately 08:00 a.m.)

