19.3. Randomisation

The randomisation table will be provided by Novagenix. **30 subjects**, who will be included in the study, will be determined to receive either Test or Reference Product [In each study period, subjects will take different products (one dose of Test Drug or one dose of Reference Drug)] by a randomisation table.

30 subjects, who will be included in the study, will be determined to receive either Treatment A or Treatment B in Period I and Period II by a randomisation table generated by a computer programme. Which one of the Test or Reference administration will be Treatment A or Treatment B is randomised by the Investigator. All the analytical analyses are done without the knowledge of the Test and the Reference product. These products will be named and known as Treatment A or Treatment B by CRO. Then the form defining Treatment-Period relationship will be enveloped, sealed and sent to CRO by the Investigator. CRO will open the sealed envelope in the "Project Evaluation Meeting" which will be held after the laboratory analyses are completed. Once the seal is opened, no new reanalyse or no data change/exclusion will be allowed.

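### Does a randomisation mark on screening day, before the Day 0 eligibility checks, with isolation losses not replaced, weaken the trial?

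*Combined protocol and SAP*

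**What the plan says.** Section 6 has one row labelled "Randomisation", marked only in the first-day (screening) column. The same chart marks the PCR test and the inclusion criteria on screening day and again on the fifth day (Day 0).

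Section 11.1 states "Only volunteers fulfilling all of the following criteria should be enrolled in the present trial", and its third criterion asks for two negative PCR results. The footnote reads "One of the Covid-19 PCR test will be applied on examination day, the other will be applied on the" fifth isolation day. Section 13.3 agrees: "Covid-19 PCR test will be done at Day 0".

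Section 13.4 adds: "Upon admission to the clinic for study, all volunteers will undergo an alcohol breath test and drug screening in the urine", with discontinuation after a positive result. The flow chart and Section 13.1 place those two tests at screening.

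Three sections use the number 30 differently:

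- Section 14.2 enrols 30 volunteers and continues "If drop-out exists in isolation or in study period, then these dropouts" are not replaced.
- Section 10 says "30 healthy male subjects (intention to treat population) will receive one single oral dose of 200 mg favipiravir".
- Section 19.3 says "30 subjects, who will be included in the study, will be determined to receive either Treatment A or Treatment B", and gives no day for doing so.

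**The concern.** Read literally, the chart randomises volunteers who cannot yet have met every inclusion criterion, because the second PCR is still to come. Three consequences suggest themselves.

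- **An unclean randomised set.** Some randomised volunteers may never be eligible or dosed, and 30 could mean enrolled, allocated or dosed. The three sections agree only if nobody is lost in isolation.
- **Sequence imbalance.** Losses before dosing can leave the two sequences unequal in size.
- **Concealment.** The clinical phase is open-label, and under Section 19.3 the investigator decides which product is Treatment A or B. Exclusions that rest on judgement (Section 11.2, criterion 6; Section 14.1) remain possible after screening. If the sequence were known by then, it could influence who goes forward.

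In a parallel-group trial analysed by intention to treat, this would be serious.

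**Working it through.** **1. What the plan's own figure allows.** Section 19.2 gives a within-subject CV of 17% for Cmax and a sample size of 30, but no power, expected ratio or drop-out rate, so 30 cannot be reproduced. At CV 17% and an assumed true ratio of 0.95, the two one-sided tests need 14 subjects for 80% power and 20 for 90%. The 30 therefore leaves room for losses.

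**2. Which set is analysed.** Section 10 uses subjects who completed the study according to the protocol. Section 13.1 keeps withdrawn subjects out of the statistics. Section 19 analyses volunteers without major deviations for whom all primary variables are available. The intention-to-treat label in Section 10 is attached to no analysis. A volunteer lost in isolation has no concentrations and enters nothing, whether or not he was allocated.

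**3. Bias in the test/reference ratio.** Write a subject's ln-scale results as subject effect + period effect + treatment effect + error. The difference, period 1 minus period 2, has expectation

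- sequence test–reference: (period 1 − period 2) + (T − R)
- sequence reference–test: (period 1 − period 2) − (T − R)

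Half the difference between the two sequence means is T − R. The subject effect has gone, so removing undosed volunteers from one sequence because of their own characteristics leaves the estimate centred. Bias would require selection on something that predicts how a subject's response differs between two tablets not yet taken. The ANOVA in Section 19.1.2 contains period, sequence and subject within sequence, so unequal sequence sizes are handled.

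**4. Cost in precision.** Assumptions: a list balanced 15/15 (the protocol states no block size), independent losses at rate f before dosing, true ratio 0.95. The comparator is allocation on Day 0 with sequence sizes differing by at most 1.

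- Chance of at least one loss = 1 − (1 − f)^30. For f = 10%: 1 − 0.9^30 = 0.958.
- s = √ln(1 + 0.17²) = 0.1688.
- SE = s·√[½(1/n1 + 1/n2)]. For 15/15: 0.1688 × √(½ × 2/15) = 0.0436.
- Power: two one-sided tests at 5%, limits 0.80–1.25, n1 + n2 − 2 degrees of freedom, averaged over the binomial losses.

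| Pre-dose loss f | At least one lost | Expected number dosed | Sequences differ by ≥2 | Mean variance cost of early allocation | Mean power, early / Day 0 |
|---|---|---|---|---|---|
| 2% | 45% | 29.4 | 5% | 0.03% | 98.44 / 98.44% |
| 5% | 79% | 28.5 | 19% | 0.13% | 98.15 / 98.16% |
| 10% | 96% | 27.0 | 35% | 0.33% | 97.54 / 97.58% |
| 20% | 99.9% | 24.0 | 49% | 0.84% | 95.75 / 95.89% |

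The expected number dosed does not depend on when allocation is done: a volunteer lost in isolation is lost either way.

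**5. A harsher case.** Suppose four are lost, all from one sequence, giving 15/11 instead of 13/13. The variance ratio is (1/15 + 1/11)/(2/13) = 0.15758/0.15385 = 1.024. At an assumed CV of 25% and ratio 0.95, power is 76.6% for 15/11 and 77.6% for 13/13. Going from 30 to 26 subjects costs far more (83.4% to 77.6%), and later allocation would not recover it.

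**The case for a change.** The strongest reply is that the value lies in a defined randomised set and in concealment, not in power. Other text also fits early allocation: Section 11.4 makes the screening number the subject code, and Section 13.5 doses subjects in ascending order by the randomisation list. If the list is keyed to that code, sequence is fixed at screening. The conflict among Sections 10, 14.2 and 19.3 stands whatever the mark means.

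Part of this holds. The second PCR and the Day 0 re-check do come after the marked day, and 30 is used loosely. Three things limit the weight of it.

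- **The timing rests on one table mark.** Section 16.1 files volunteers who were screened but never randomised, so randomisation follows a screening outcome. Section 19.3 gives no day, and Appendix VII, which governs the interval, is not in the supplied text. The mark may record only a number linked to a prepared list. The admission tests are weaker support, since the documents disagree on when they are done.
- **Early knowledge of the sequence is not shown.** Section 12.2.1 says the investigator will know the products, but not from when. Discretionary withdrawal also continues after dosing, so a later mark would close only part of that route. Securing near-equal sequences on Day 0 through very small blocks would make many allocations predictable in an open-label trial.
- **Section 14.2 is the specific rule.** By refusing to replace isolation losses, it accepts that fewer than 30 may be dosed. The other two sections read naturally as planned numbers.

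**Conclusion.** No change is needed. The chart's timing is loose and the number 30 is used in more than one sense, but following the plan as written gives the same analysis set, an unbiased test/reference contrast and practically the same precision as allocation after the Day 0 checks. The differences are at most 0.84% in mean variance and 0.14 points in mean power, even at an assumed 20% pre-dose loss. Site staff and analysts can apply Section 14.2 directly: those still eligible on Day 0 are dosed, and those who complete are analysed. Even 24 dosed is twice the minimum of 12 set in Section 19.1.2.

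This rests on the 17% CV in Section 19.2, an assumed true ratio of 0.95, assumed independent loss rates and a balanced list. A larger CV or a ratio nearer 0.90 would make lost volunteers more costly, but when allocation is done would still have little bearing on that cost. The bias argument assumes that pre-dose exclusions are unrelated to how an individual's response would differ between the two tablets.
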